Official Title:	The Use of a Consumer-Based mHealth Dietary App and Health Coaching with Kidney Transplant Recipients Study Information
NCT Number:	NCT05151445
Document Name:	Study Protocol and Statistical analysis Plan
Document Date:	05/05/2021

Study/Project Title: The Use of a Consumer-Based mHealth Dietary App and Health Coaching with Kidney Transplant Recipients

I. Objectives

The purpose of the study is to test the feasibility mHealth dietary app + health coaching for improving primary outcomes (recruitment, retention, and adherence) and secondary outcomes (perceived stress [Perceived Stress Scale], exercise self-efficacy[Exercise Self-efficacy Scale], vegetable intake [Fruit, Vegetables, and Fiber Screen] fat intake [Lose-it Premium database], carbohydrate intake [Lose-it Premium database], weight, blood pressure [Wi-Fi weight scale using the Lose-it Premium database], heart rate [Wi-Fi blood pressure cuff using the Lose-it Premium database], and the minutes of physical activity per day [Lose-it Premium database])

Background and Rationale Weight gain and obesity are common after kidney transplant, often leading to the development of cardiovascular disease, post-transplant diabetes, and death.¹ The increase in weight gain during the first year after transplant is associated with the use of immunosuppressive medications, and changes in lifestyle, such as dietary intake and insufficient physical activity. Moreover, weight gain is affected by factors such as, age, sex, race, and stress.² Evidence indicates that kidney transplant recipients who gain less weight after transplant are physically active, consume fewer carbohydrates, consume more vegetables, and experienced less stress.³ Further, limiting dietary fat and increasing post-kidney energy expenditures aid in preventing early insulin resistance and cardiovascular disease.^{4 5}

However, few studies have tested dietary and physical activity interventions using real-time mobile health applications (mHealth) to enhance lifestyle self-management of care with kidney transplant recipients.⁶

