Our proposed study seeks to shift the paradigm for promoting diet intake and physical activity using education and self-report to provide a powerful combination of mHealth dietary app and health coaching (set goals, provide ongoing feedback, and self-monitor behaviors). To our knowledge, this is the first time a mHealth dietary app and health coaching intervention has been used in kidney transplant recipients to link real-time data for monitoring dietary intake and physical activity.

The long-term goal of this work is to enhance well-being in kidney recipients via lifestyle self-management of care for dietary intake and physical activity to ultimately prevent chronic diseases. The proposed study is important because early weight gain after kidney transplant is associated with adverse effects on the transplanted kidney function resulting in increased health care cost and poor quality of life.⁷ Interventions are needed to monitor kidney transplant recipients diet and physical activity in real-time to prevent health decline.

The goal of the proposed feasibility study is to recruit a sample (N = 20) of post-kidney transplant recipients (age 18 and above) who will receive the mHealth dietary app + health coaching intervention for 12 weeks. We will assess changes over time for the primary outcome and secondary outcomes from baseline to 4, 8, and 12 weeks. We plan to submit our findings for publication to the Journal of Progress of Transplantation (Impact factor 0.958) or Trends in Transplantation (Impact factor 0.1.69). We *hypothesize* that the mHealth dietary app + health coaching intervention will improve adherence for recording diet and physical activity, decrease perceived stress, increase exercise self-efficacy, increase vegetable intake, decrease fat intake, decrease carbohydrate intake, improve weight control, improve blood pressure control, improve heart rate and an increase the number of minutes of physical activity per day. We will

also examine biological differences among the secondary outcomes of perceived stress, exercise self-efficacy, vegetable intake, fat intake, carbohydrate intake, weight, blood pressure, heart rate and minutes of physical activity per day, as previous studies have reported differences in outcomes based on age, sex, and race.^{8,9} The rationale for our hypothesis is that progression of cardiovascular disease and chronic disease may be slowed with daily tracking of dietary and physical activity.

II. Procedures

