The procedures should include the following:

A. Research Design

A feasibility study will be utilized to establish the recruitment, retention, and adherence with post-kidney transplant recipients using a consumer-based mHealth dietary app + health coaching.

B. Sample

Inclusion Criteria

(a) age 18 or older men and women, (b) functioning KTR (not on dialysis), (c) ability to speak, read, and hear English, (d) possession of a smartphone capable of accessing and downloading a mHealth dietary app (e) Wi-Fi or Internet access, (f) greater than 3 months post-transplant (due to medication adjustments and decreased functional levels), (g) not hospitalized, and (h) capable of self-consent per capacity screening.³²

Exclusion Criteria

(a) Participation in a weight loss program, (b) participation in a structured exercise program, and (c) diagnosis of dementia.

How will subjects be selected?

The participants will be recruited or contacted from a list of kidney recipients that have already requested they be contacted for future studies from our previous study (**IRB Protocol Number: 2017B0084**). This list consists of approximately 60 people. This study will also be advertised at the Ohio State University Medical Center Kidney Transplant monthly support group. Fliers with study information will be made available at the support group. The support group leader will also inform the group participants about the study.

After participants meet the initial screening requirements in the recruitment process, we will determine capacity to obtain verbal consent using the Evaluation to Sign Consent Form (ESC). The ESC consists of five questions (“What are risks associated with the study?” “What are two potential risks for participating in the study?” “What is expected from you in this study?” “What if you do not want to continue the study?” “What if you experience discomfort?”) and takes less than 10 minutes to complete. The ESC allows the participant to reflect upon their understanding of the research protocol by answering the five questions. Participants must answer all five questions correctly to be included in the study. Anybody who is able to answer all five questions correctly will then be read verbal consent script by the study team.

C. Measurement / Instrumentation

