Participant **Demographic Information** (10 minutes) will be obtained using a seven-item questionnaire demographics form and **Comorbidity Data** will be gathered using the Charlson Comorbidity Index³³ to describe the patient population. **Aim 1: Recruitment** (percent approached),

will be recorded in REDCap by the RA. **Retention** (percent dropped) will be recorded in REDCap by the RA. **Adherence** (percent to adhere to logging daily dietary intake and physical activity) will be recorded continuously each day by the “Lose-It” app. **Aim 2: Perceived Stress** (10 minutes) will be evaluated by using the Perceived Stress Scale (PSS).³⁵ The PSS is a 10-item questionnaire using a Likert Scale to rate feelings of stress from 0 “never” to 4 “very often.” The PSS has demonstrated excellent test-retest reliability (intraclass correlation coefficient = 0.954) and internal consistency (Cronbach's alpha = 0.810) with adults who have chronic disease.³⁶ **Exercise Self-Efficacy** (10 minutes) will be evaluated by using the Self-Efficacy for Exercise (SEE) Scale. The SEE is a 9-item questionnaire using a Likert Scale to rate feelings of stress from 0 “not confident” to 10 “very confident.” The SEE has demonstrated excellent internal consistency ($\alpha = 0.92$) for adults living with chronic disease.³⁷ **Vegetable intake** will be measured using the Block Fruit-Vegetable-Fiber Screener. The Block Fruit-Vegetable-Fiber Screener (5 minutes) has demonstrated high reliability (Spearman r -value of 0.71).³⁸ This brief screening tool includes seven questions about fruit and vegetable intake and three questions about foods high in fiber, magnesium, and potassium. **Fat Intake and Carbohydrate Intake** (5 minutes) will be recorded each day by the participant using the “Lose-It” app. **Weight** will be measured each day by the participant using a wireless Wi Fi weight scale. The data from the wireless weight scale will sync the data from the participant's mobile phone to the premium password-protect “Lose-It” database each day. **Blood Pressure and Heart Rate** will be recorded each day by the participant using a wireless Wi Fi blood pressure cuff. The data from the wireless cuff will sync from the participant's mobile phone to the premium password-protect “Lose-It” database each day. **Minutes of Physical Activity per Day** will be recorded each day by the participant using the “Lose-It” app. **Clinical Frailty Scale** (5 minutes) will be used to measure the frailty level of each participant. The screening tool has demonstrated high reliability in adults. This brief screening tool consist of nine questions about a person's level of frailty.

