Descriptive statistics will be used to summarize sample characteristics. **Aim 1)** percent approached, percent dropped, and percent to adhere to logging daily dietary and physical activity will be analyzed using means and standard deviations of these variables and analyzed as differences between the baseline and 3-month measurements using the Wilcoxon Signed-Ranked test. **Aim 2)** Perceived Stress Scale, Exercise Self-efficacy Scale, Fruit, Vegetables, and Fiber Screener, fat intake, carbohydrate intake, weight, blood pressure, heart rate, and the minutes of physical activity per day will be analyzed using the differences among baseline, 4, 8, and 12 weeks using repeated measures analysis of variance using the Friedman's Test. Frailty levels will be collected at baseline and 12 weeks and will be analyzed using means and standard deviations of this variables. **Missing Data:** We will carefully record and code various reasons for missing data (e.g., participants forgot to record data into the "Lose-It" app) and examine the pattern of missing data.

III. Bibliography

2. Aksoy N. Weight Gain After Kidney Transplant. *Exp Clin Transplant.* 2016;14(Suppl 3):138-140.

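### Recruitment, a primary outcome, is measured only as the percentage approached and is assigned a paired test that cannot be applied to it

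*Combined protocol and SAP*

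**What the plan says.** Section I (Objectives) lists the "primary outcomes (recruitment, retention, and adherence") that the study will assess. Section II.A gives the purpose of the design: "A feasibility study will be utilized to establish the recruitment, retention, and adherence". The enrolment goal, stated in the background, is to "recruit a sample (N = 20) of post-kidney transplant recipients".

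Section II.B (How will subjects be selected?) names two sources. The first is "a list of kidney recipients that have already requested they be contacted for future studies from our previous study", and its size is given: "This list consists of approximately 60 people". The second is a kidney transplant support group, reached by fliers and through the group's leader. No group size, attendance figure or record of people told is mentioned for it.

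Section II.C (Aim 1) gives the recruitment measure as "percent approached", recorded in REDCap by the research assistant (RA). Section II.F (Aim 1) takes "percent approached, percent dropped, and percent to adhere to logging daily dietary and physical activity" together, to be summarised by means and standard deviations and "analyzed as differences between the baseline and 3-month measurements using the Wilcoxon Signed-Ranked test". Neither section gives a numerator or a denominator for recruitment, and neither says whether the two sources are reported together or apart.

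**The concern.** A feasibility study that sets out to establish recruitment needs a measure of how many people take part among those asked. The stated label describes how many people the team contacted. That is effort, and it need not move with uptake.

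The planned analysis does not rescue the measure. A signed-rank test compares two measurements on the same unit. Recruitment is a single proportion for the whole study and has neither a baseline nor a 3-month value. Taken as written, one primary outcome has a measure that does not show uptake and an analysis that cannot be run.

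Reading the label as shorthand for enrolled divided by approached helps only in part. The list can be counted, but the plan provides for no count of people reached through the support group, so the denominator of an overall rate is left open. Section II.E says the study will inform a larger multisite trial, and an undefined rate is a weak basis for planning one.

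**Working it through.** **Inputs.** From the documents: target enrolment 20 (background, study goal); contact list of about 60 (section II.B). Not in the documents, and assumed below: how many list members are contacted, how enrolments split by source, and how many people are reached at the support group. The plan states no recruitment rate or target percentage, so there is no figure to reproduce.

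**1. Literal reading: contacted / list.**

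- All 60 contacted: 60/60 = 100%. Uptake could be 5/60 = 8.3% or 20/60 = 33.3%; the measure is 100% in both cases.
- With 20 enrolled after 30 contacts: measure 30/60 = 50%, uptake 20/30 = 66.7%. With 20 enrolled after 60 contacts: measure 100%, uptake 33.3%. Here the measure rises while uptake falls.

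**2. The assigned analysis.** The signed-rank test uses differences d_i = (3-month value) − (baseline value), one per participant. Recruitment is one number for the study, so there are no pairs. The mean of one number is that number, and its sample standard deviation has divisor 1 − 1 = 0. Coding enrolment as 1 for each enrolled participant does not help: every value is 1 at both times, every d_i is 0, and nothing is left to rank. This holds however the label is read.

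**3. Enrolled / approached, if one overall rate were formed.** Assume all 60 list members are contacted and 20 people enrol in total. Let k be enrolments from the support group and s the number of group members counted in the denominator.

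- Overall rate = 20/(60 + s)
- List uptake = (20 − k)/60

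| k | s | Overall rate | List uptake | Difference (points) |
|---|---|---|---|---|
| 0 | 0 | 20/60 = 33.3% | 20/60 = 33.3% | 0 |
| 5 | 0 | 20/60 = 33.3% | 15/60 = 25.0% | +8.3 |
| 10 | 0 | 20/60 = 33.3% | 10/60 = 16.7% | +16.7 |
| 5 | 20 | 20/80 = 25.0% | 15/60 = 25.0% | 0 |
| 5 | 40 | 20/100 = 20.0% | 15/60 = 25.0% | −5.0 |

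The sign depends on k and s, and the documents give neither.

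**4. Precision of the proposed measure.** Exact (Clopper-Pearson) 95% limits for x of n are the 0.025 quantile of Beta(x, n − x + 1) and the 0.975 quantile of Beta(x + 1, n − x).

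- 20/60 = 33.3%: 21.7% to 46.7% (width 25.0 points)
- 15/60 = 25.0%: 14.7% to 37.9% (width 23.1 points)
- 10/60 = 16.7%: 8.3% to 28.5% (width 20.2 points)

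**5. Why the denominator has to be written down.** If, as a further assumption, 25 people were known to meet the initial screening requirements and 20 consented, the rate on that base would be 20/25 = 80.0% (59.3% to 93.2%), against 33.3% on the base of all 60 contacted.

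**The case against.** The label is probably shorthand. The retention label beside it is equally terse, and the team may well mean enrolled out of approached. This is a fair reading, and it makes the 100% scenario a consequence of following the text rather than a forecast of what will be reported. It still leaves the denominator unstated, and it does nothing for the Wilcoxon assignment.

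A reader might infer that the plan will pool the two sources and so overstate uptake. The documents do not support that. No section says the sources will be pooled. Attendance at a support group could be counted, although the plan does not provide for it. As the last row of the table shows, a combined rate that includes attendees can fall below the list rate.

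A reader might also infer that the list rate would be lost unless each enrolment were tagged by source. That goes too far as well. The list already exists, so enrolled participants can be matched to it afterwards. What matching cannot supply is which list members were contacted.

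Two further points limit the consequence. The plan sets no recruitment-rate threshold or progression rule, and its one recruitment benchmark, 20 participants, is a count that needs no denominator. Also, if every list member is contacted, the list is fully enumerated, and the interval has meaning only if the list is treated as a sample of similar recipients willing to be contacted. Both points stand. They bear on how much weight the rate can carry, but do not remove the need to define it.

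**Conclusion.** The point holds as a defect in how a primary outcome is defined and analysed. Two parts need no assumption about the label or the sources: no numerator or denominator is given, and the assigned paired test cannot be applied to recruitment. The uninformative 100% follows only if the label is taken literally and the whole list is contacted.

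Bias from a combined rate is conditional on the sources being pooled, and its direction is open. The differences from −5.0 to +16.7 points illustrate assumed splits and group sizes and are not estimates. Participant safety and the Aim 2 analyses are unaffected, and much of the list rate could be reconstructed if contacts are logged. The correction should be made because it is nearly free and concerns something the study exists to establish.

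**What to change.** In sections II.C and II.F (Aim 1):

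- Define recruitment, for the contact list, as number consented divided by number contacted. Report it as a proportion with an exact 95% confidence interval, and state that it applies to people who had already asked to be contacted.
- Report support-group recruitment separately, as counts of people who responded, were screened and enrolled.
- In section II.F, take recruitment out of the sentence on means, standard deviations and the Wilcoxon signed-rank test.
- Have the RA log in REDCap which list members were contacted.

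A source tag on each recruitment record, and a second ratio of consented to known eligible, are optional.

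The cost is a change of wording in two places and slight extra logging in a record the RA already keeps. The downside is a wide interval, about 20 to 25 percentage points for 10 to 20 consenting out of 60.

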
D. Detailed study procedures

The “Lose-It” app will be set up with Gmail accounts with unique unidentifiable codes developed by the research team. Participants will be instructed how to download the “Lose-It” app virtually using Zoom. In addition, participants will be taught how to sync to their smartphone and retrieve data from their app. The participants will be trained to enter their dietary intake and physical activity daily for 12-weeks.

Participants will monitor their vegetable intake, fat intake, carbohydrate intake, weight, blood pressure, heart rate and the minutes of physical activity per day using the “Lose-It” app. Wi-Fi connected weight scales and blood pressure cuff will be supplied for weight and blood pressure monitoring. Participants will be taught how to sync the data from the scales and blood pressure cuff to the “Lose-It” app using the Premium database which will Sync all of the data into password protected database for the research team to access. Participants will perform a return demonstration to confirm that they can record their dietary intake daily, physical activity, weight, and blood pressure using the “Lose-It” app. We also review with the participant the “My Plate” method for proper nutrition and the steps to distance conversion chart. Each participant will be given a copy of both via email.

Session	mHealth App + Health Coaching Intervention Setting: Online video- conference call (Zoom)
Baseline Session (Session 1)	The research assistant (RA) will demonstrate proper “Lose-It” app use, set up the smartphone application, and how to enter their dietary intake, physical activity, weight, blood pressure, heart rate and the minutes of physical activity per day using the “Lose-It” app. The RA will demonstrate how to sync the data from the Wi Fi weight scales and blood pressure cuff to the “Lose-It” app.
Time for session: 90 minutes	Participants will perform a return demonstration to confirm that they can access the “Lose-It” app, sync the data from the Wi Fi scales and blood pressure cuff.

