Week 1-12 (Sessions 2-13) Time for session: 30 minutes	
Phase 1: The participant will place the goals (dietary and physical activity) into their “Lose-It” app via smartphone for goal attainment.
 
Phase 2: The participant and the RA will review the electronic report generated from the “Lose-It” app for monitoring or assessing progress for dietary intake and physical activity each week from baseline to week 12.
 
Phase 3: The RA will review with the participant each week for 12 weeks how many days they implemented and achieved the solution for their daily goals.
 
Phase 4: Time will be allowed for any questions.

Risk and Benefits

The risks for harm to you for participating in this study are minimal. You may feel uncomfortable about having the research team knowing about your dietary intake or physical activity level. It is not unusual for people with a transplant to occasionally have difficulty with being physically active and controlling their weight. We are trying to help people with these common problems.

If you agree to take part in this study, there may or may not be direct medical benefits to you.

We hope the information learned from this study will in the future benefit other patients with a kidney transplant who are having difficulty becoming physically active and assessing their dietary intake.

E. Internal Validity

In the previous K award²² study, we found that the primary reason for participants not enrolling (65%) into the study was due to the distance of traveling to the research site. Thus, there is a need to deliver the intervention activities in home settings via Zoom. The delivery of our study research activities is timely due to the Coronavirus (COVID-19) and the fact that our population is immunocompromised. Due to the recent pandemic outbreak of the coronavirus (COVID-19) and since our population is immunocompromised. We will promote sustainability for participating in the study by sending weekly text messages to the participants to thank them for their participation in the study. The conduct of this feasibility study will help identify other limitations to consider for future studies in a larger multisite clinical trial. We will collect data regarding the time spent on delivering the intervention so that we can conduct a cost-effective analysis at a later date.

F. Data Analysis

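### Adherence, a primary outcome, is one percentage for diet and activity logging together, with no rule for what counts as a logged day, how a rest day is marked, or what the denominator is

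*Combined protocol and SAP*

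**What the plan says.** Section I (Objectives) names recruitment, retention and adherence as the primary outcomes. The whole definition of adherence is in II.C (Measurement / Instrumentation, Aim 1): "percent to adhere to logging daily dietary intake and physical activity) will be recorded continuously each day by the “Lose-It” app". II.F (Data Analysis, Aim 1) treats it as one variable: "percent to adhere to logging daily dietary and physical activity will be analyzed using means and standard deviations of these variables".

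Three other statements bear on how it should be read:

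- The hypothesis in the Background and Rationale describes recording behaviour. It says the intervention "will improve adherence for recording diet and physical activity".
- The same hypothesis lists amount of activity as a separate effect: "an increase the number of minutes of physical activity per day". Minutes per day is a secondary outcome taken from the same app.
- II.D (Detailed study procedures) sets the expected frequency and duration: "The participants will be trained to enter their dietary intake and physical activity daily for 12-weeks".

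II.F also plans to code the reasons for missing data, with forgetting to make an app entry as the example. It does not connect that coding to the adherence score.

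**The concern.** One percentage covers two behaviours for which a blank day means different things. People eat every day, so a day without a diet entry is almost always missed logging. A day without an activity entry may be missed logging or a day with no activity. The protocol does not tell participants to enter a zero, and an analyst looking at the app data later cannot reliably tell the two apart.

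The scoring rule is also open. If a day needs both entries and rest days are blank, an inactive participant who records everything loses credit on each rest day, and the score rises when people become more active even if their recording is unchanged. If either entry is enough, someone who logs diet daily and never logs activity is fully adherent. Neither version isolates recording.

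The denominator is a further gap. Days after a participant stops could be left out or counted as not logged, and the two choices give different answers.

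Minutes of physical activity per day is affected in the same way, because a blank could be analysed as zero or as missing.

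**Working it through.** The documents state no adherence figure, target or power calculation, so there is no figure of theirs to reproduce. The check is how far the score for fixed behaviour moves with the unstated rules.

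**Inputs from the documents:** daily entry for 12 weeks, so 12 × 7 = 84 days (II.D); planned sample N = 20 (Background and Rationale).

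**Assumed inputs:** the number of inactive days per week, k, from 1 to 5; and, for the denominator, the number who stop, when they stop, and the logging rate while in the study. The documents give none of these.

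**Step 1: day-level rule.** Take a participant who logs diet on all 84 days and logs every activity that occurs. Inactive days number 12k.

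- Both entries required, rest days blank: (84 − 12k)/84.
- Average of the diet and activity percentages, rest days blank: [1 + (84 − 12k)/84]/2.
- Zero entries count as logged, or either entry is enough: 84/84.

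| Inactive days per week (k) | Both required, rest days blank | Average of the two | Zero counts, or either entry |
|---|---|---|---|
| 1 | 72/84 = 85.7% | 92.9% | 100% |
| 2 | 60/84 = 71.4% | 85.7% | 100% |
| 3 | 48/84 = 57.1% | 78.6% | 100% |
| 4 | 36/84 = 42.9% | 71.4% | 100% |
| 5 | 24/84 = 28.6% | 64.3% | 100% |

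In active days per week, the second column gives 2/7 = 29%, 3/7 = 43% and 5/7 = 71%. Moving from 3 to 5 active days would lift the score from 43% to 71% with no change in recording.

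**Step 2: denominator.** Suppose s of 20 participants stop at week 4 (28 days) and everyone logs 80% of days while in the study. Over days in study the mean is 80% whatever s is. Over 84 days for all 20, with days after stopping counted as not logged, the mean is [(20 − s) × 0.80 + s × 0.80 × 28/84]/20.

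- s = 3: (13.6 + 0.8)/20 = 72%
- s = 5: (12.0 + 1.33)/20 = 66.7%
- s = 6: (11.2 + 1.6)/20 = 64%

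**The case against.** A reader might infer that a faithful logger with inactive days is scored as non-adherent. The documents do not support that. No section says that a day needs both entries or that a blank activity day fails. II.D trains participants to enter activity daily, and II.C has minutes recorded each day; both are compatible with entering zero on a rest day, in which case a blank really is a missed log. The 43% example needs participants to leave rest days blank, and the protocol does not tell them to do so.

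A reader might also infer that the study could not show whether daily logging is feasible. That is too strong. Diet entries sync to a database that the team can access, so diet logging can be computed on its own without new data. The research assistant also reviews the app report with each participant weekly (Sessions 2–13), and reasons for missing data are to be coded. These steps could help separate forgotten entries from rest days.

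The size rests wholly on assumptions. The Risk and Benefits text, "It is not unusual for people with a transplant to occasionally have difficulty with being physically active and controlling their weight", makes inactive days plausible but gives no frequency and says nothing about scoring. Counting days after dropout as not logged is partly a preference, since retention is already a primary outcome and dropout would then weigh on both. The documents do not say whether the app can store a zero. With 20 participants, one group and no adherence target to pass or fail, the practical consequence is limited.

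All of this stands, but it does not remove the gap. Being compatible with a zero entry is not an instruction to make one. Neither the weekly review nor the missing-data coding is tied to the score, and a blank not resolved at the time cannot be reliably resolved afterwards.

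**Conclusion.** The point holds as a missing operational definition of a primary outcome. The plan does not fix what a logged day is, how a rest day is marked, or what the denominator is.

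Under one plausible combination, both entries required and rest days blank, a faithful logger can score anywhere from 28.6% to 85.7% for 5 to 1 inactive days a week. With zeros counted, the same behaviour scores 100%. Under that combination the measure partly reflects being active and not only recording. The denominator choice adds a separate difference: 80% against 72%, 67% or 64% when 3, 5 or 6 of 20 stop at week 4. These figures show sensitivity to unstated rules. They do not predict the result, because the active-day counts, stopping pattern and 80% logging rate are all assumed.

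The change should be made before data collection. The zero-entry instruction alters what is collected, so a later analysis decision cannot fully replace it.

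**What to change.** 1. In II.C and II.F, replace the single percentage with two: percent of days with diet logged and percent of days with activity logged.
2. In the existing Session 1 training, tell participants to enter 0 minutes on inactive days. If the app cannot store a zero, confirm rest days at the existing weekly review of the app report and record them. Either way a blank then means not logged, which also settles how blanks are treated in minutes of activity per day.
3. Report both percentages over 84 days for every enrolled participant, with days after stopping counted as not logged. Show the while-in-study percentage beside each, labelled as such, because retention is already a separate primary outcome.

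The cost is protocol wording and one instruction in a session that already exists. The downsides are one small extra entry on rest days and an adherence figure that may look less favourable.
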